#### 6.4 Sample Size and Power

This study aims to enroll 110 ALL cohort subjects across several centers for Aims 1 and 2. The complexity of specimen processing for Aim 2b will limit performance of these assays to approximately 40 of the overall 110 subjects.

For Aim 1, a cohort of 330 matched healthy control patients will be assembled for the purpose of comparison of infection incidence rates in healthy patients versus those who recently completed ALL therapy. Based on preliminary data collected on this study's cohort of ALL patients, the infection incidence rate in the first year after completion of chemotherapy is estimated to be 1.88 events per person-year. For this power calculation, we assume the rate of infection for the entire ALL cohort will mirror the currently estimated rate of 1.88 events per person-year, assume a two-sided type I error of 0.05, and range the values of overdispersion parameter from 1 to 3.

With 50 ALL patients and 150 matched healthy participants (1:3 match) and one year of follow up on each participant, the detectable effect size with at least 80% power is summarized in Table 1. For example, under the assumption of no overdispersion (overdispersion parameter=1), we will have 80.1% power to detect an IRR of 1.45, i.e., incidence rate of 1.88 for cancer cohort vs. 1.30 for healthy cohort. Under the conservative assumption of a larger overdispersion parameter of 3, we will have 80% power to detect an

IRR of 1.90, i.e., incidence rate of 1.88 for cancer cohort vs. 0.99

for healthy cohort. Although we do not have an accurate estimate of the event rate in the healthy cohort, an IRR in the range of 1.45 to 1.90 represents

a clinically meaningful effect size for which we will have sufficient power to detect.

**Table 1.** Power calculation Across Multiple Estimates of Baseline infection Event Rate, Detectable Incidence Rate Ratios, and Overdispersion Parameters

Infection event rate in the healthy cohort	IRR	Overdispersion parameter	Power
1.30	1.45	1	80.1%
1.19	1.58	1.5	81.0%
1.11	1.69	2	80.1%
1.04	1.81	2.5	81.2%
0.99	1.90	3	80.0%

The descriptive and comparative results from Aim 1 will provide important point estimates for infection in the first year post ALL chemotherapy that clinicians can use to manage family expectations for this recovery period.

Outcomes for Aim 2 are descriptive and thus power calculations are not provided. The point estimates for seroprevalence will inform if children retain protection against specific pathogens from vaccination administered prior to their diagnosis of and treatment for ALL. Point estimates for seroprevalence will be described for the entire cohort and by subsets of patient characteristics (e.g., chemotherapy inclusive of blinatumomab). The trajectory of recovery of B and T cell subsets will also be described for the sub-cohort of patients enrolled at CHOP. Differences in trajectories by patient specific characteristic (e.g., chemotherapy inclusive of blinatumomab) will also be explored. These granular descriptive immune function data will inform the need for revaccination in this patient population and if necessary, will provide guidance for the optimal design of revaccination studies.

---

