#### **3.2.2 Total Number of Study Sites/Total Number of Subjects Projected**

The study will be conducted at seven investigative sites in the United States. Other sites may be added in the future. It is expected that approximately 115 subjects will be enrolled over the course of this study to produce 110 evaluable subjects. Evaluable patients will be defined as patients that are enrolled and at least one blood specimen collected.

For each of the 110 enrolled evaluable subjects in the ALL cohort, at the end of the follow-up period, three age- and sex-matched healthy control patients will be selected for comparison, to assemble a cohort of 330 total healthy control patients. The full cohort,

---

including both ALL patients and 3:1 matched controls, is anticipated to include 440 evaluable patients.

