### 6.3 Statistical Methods

#### 6.3.1 Baseline Data

Baseline and demographic characteristics will be summarized by standard descriptive summaries. Categorical variables will be summarized by frequencies while continuous variables will be summarized by using mean, standard deviation, median, twenty-fifth and seventy-fifth percentiles, minimum and maximum.

#### 6.3.2 Analysis of Aim 1

Aim 1 (total number of unique infections identified within the first year after completing chemotherapy) will be reported as a rate per 1000 follow-up days. This rate will be reported for the entire cohort, by study site, and by demographics (e.g., age, race, gender). This outcome will also be reported within subsets of infection type (i.e., microbiologically documented infections and bacterial sinopulmonary infections) also reported as a rate per

---

1000 follow-up days for the entire cohort, by study site and by specific demographic variables. All infection rates will be reported as a post estimate with 95% confidence intervals. Patients will be censored at time of lost to follow-up or death.

Infection rates for enrolled patients will also be compared to those of controls matched on age and sex selected from the CHOP Pediatric Research Consortium (PeRC). Three healthy controls will be selected for each participant for a case to control ratio of 1:3. Control patient infection data will be obtained for the same follow-up time period as that of the matched case patient in order to match risk for infection from seasonal pathogens (e.g., if a case patient completed ALL therapy and enrolled in the study in January 2023, infection data for the matched controls would be collected from January 2023 through December 2023, the same follow-up period as that of the case patient). All control patients will be randomly selected, and control data will be collected when follow-up is complete for participants in the ALL cohort.

Infection rates will also be generated for patients who received blinatumomab as part of their chemotherapy regimen and those who did not receive blinatumomab.

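### Section 6.4 and Table 1 compute power for 50 ALL patients and 150 controls, but the plan is 110 and 330; the stated powers are too low and the detectable rate ratios too large for the planned design

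*Combined protocol and SAP*

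**What the plan says.** Section 6.4 opens with the full cohort: "This study aims to enroll 110 ALL cohort subjects across several centers for Aims 1 and 2". It continues, "For Aim 1, a cohort of 330 matched healthy control patients will be assembled". Section 3.2.2 agrees. It expects that "approximately 115 subjects will be enrolled over the course of this study to produce 110 evaluable subjects", adds three controls for each of the 110 "to assemble a cohort of 330 total healthy control patients", and says that the full cohort, "including both ALL patients and 3:1 matched controls, is anticipated to include 440 evaluable patients". Section 6.3.2 repeats the matching rule: "Three healthy controls will be selected for each participant for a case to control ratio of 1:3".

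The power calculation in section 6.4 takes an ALL infection rate of 1.88 events per person-year, a two-sided type I error of 0.05, and an overdispersion parameter from 1 to 3. On the rate, it says "we assume the rate of infection for the entire ALL cohort will mirror the currently estimated rate". The next paragraph then fixes the sample size: "With 50 ALL patients and 150 matched healthy participants (1:3 match) and one year of follow up on each participant". Table 1 rests on that size. Its 80% to 81% power figures go with IRRs of 1.45, 1.58, 1.69, 1.81 and 1.90, and the text concludes that power is sufficient for this range.

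**The concern.** The power calculation should describe the comparison that the protocol plans. Here the two differ by 60 ALL patients (110 − 50) and 180 controls (330 − 150). The sizes 50 and 150 occur only in the power paragraph. No subset, interim look, attrition allowance or deliberate safety margin is given as a reason. The named subgroups do not fit either: the blinatumomab sub-cohort is 20–25 patients and the cellular immunophenotyping subset is about 40. Planned attrition is only from 115 to 110.

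Two things are at stake.

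- **The detectable effect.** Section 6.4 admits that it has no accurate estimate of the healthy-cohort rate, so the detectable IRR range is the main guide to what the comparison can show. As written, it suggests that a healthy rate above 1.30 per person-year is out of reach at 80% power even without overdispersion.
- **The scope of the comparison.** A reader cannot be sure whether it covers all 110 patients or a part of them. That also decides whether 150 or 330 control records are drawn under the requested waiver of consent.

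**Working it through.** **Inputs, all from section 6.4.** ALL rate λ₁ = 1.88 per person-year; healthy rates λ₀ as in Table 1; two-sided α = 0.05 (z = 1.96); one year per person; 1:3 ratio. Overdispersion φ is read as variance = φ × mean, because section 6.4 equates the value 1 with no overdispersion. The other common reading, variance = mean + k × mean², gives 43% to 54% at 50/150 and cannot be what Table 1 used.

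**Formulas.** The test is not named, so two standard ones were used.

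- Test A, Wald test on the log IRR: SE = √[φ(1/(n₁λ₁) + 1/(n₀λ₀))]; power = Φ(ln(λ₁/λ₀)/SE − 1.96).
- Test B, rate difference with pooled null variance: power = Φ((λ₁ − λ₀ − 1.96·SE₀)/SE₁). Here SE₀ = √[φ·λ̄(1/n₁ + 1/n₀)], λ̄ is the pooled rate, and SE₁ = √[φ(λ₁/n₁ + λ₀/n₀)].

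**Step 1: reproduce Table 1 at 50/150.** For the first row, test A has SE = √(1/94 + 1/195) = 0.1256 and ln(1.88/1.30) = 0.3689. Power is Φ(0.3689/0.1256 − 1.96) = 83.6%. Test B has λ̄ = 1.445, SE₀ = 0.1963 and SE₁ = 0.2151. Power is Φ((0.58 − 1.96 × 0.1963)/0.2151) = 81.8%.

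| φ | Healthy rate | IRR | Stated power | Test A | Test B | Simulation, robust variance |
|---|---|---|---|---|---|---|
| 1 | 1.30 | 1.45 | 80.1% | 83.6% | 81.8% | 82.0% |
| 1.5 | 1.19 | 1.58 | 81.0% | 83.4% | 81.3% | 81.8% |
| 2 | 1.11 | 1.69 | 80.1% | 82.3% | 80.1% | 81.3% |
| 2.5 | 1.04 | 1.81 | 81.2% | 81.8% | 79.4% | 81.2% |
| 3 | 0.99 | 1.90 | 80.0% | 80.2% | 77.9% | 79.6% |

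The simulation (20,000 runs, counts with variance φ × mean) is within 2 points of the stated power in every row. An exact conditional test, possible for φ = 1 only, gives 79.5%. Solving for the number of ALL patients that yields the stated powers gives 45.6–49.7 (A) or 47.7–53.1 (B). Table 1 was therefore computed at about 50, not at 110 with a mislabelled sample size.

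**Step 2: the same inputs at 110/330.** Every SE shrinks by √(50/110) = 0.674. In the first row, test A has SE = 0.1256 × 0.674 = 0.0847, and power is Φ(0.3689/0.0847 − 1.96) = 99.2%.

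| φ | Power at the tabulated IRR, A / B | IRR at 80% power, A / B | Table 1 IRR | Matching healthy rate, A / B | Table 1 rate |
|---|---|---|---|---|---|
| 1 | 99.2% / 98.7% | 1.26 / 1.27 | 1.45 | 1.49 / 1.48 | 1.30 |
| 1.5 | 99.2% / 98.5% | 1.33 / 1.34 | 1.58 | 1.41 / 1.40 | 1.19 |
| 2 | 99.0% / 98.2% | 1.40 / 1.41 | 1.69 | 1.35 / 1.34 | 1.11 |
| 2.5 | 98.9% / 97.9% | 1.46 / 1.47 | 1.81 | 1.29 / 1.28 | 1.04 |
| 3 | 98.6% / 97.4% | 1.51 / 1.53 | 1.90 | 1.24 / 1.23 | 0.99 |

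The matching healthy rate is 1.88 divided by the unrounded IRR. At φ = 3 the planned study can detect a smaller effect (1.51–1.53) than Table 1 gives for φ = 1.5 (1.58).

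**The case against.** The mismatch itself is hard to dispute. The case on the other side concerns its weight and how firmly the new figures can be stated.

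- **It does no harm.** The error is conservative. The 110 is not derived from this calculation, section 1.2 says that most of the cohort is already enrolled, and no analysis would change. This stands, and it limits the point to a correction of the text. It does not make 50/150 the planned comparison.
- **The new figures assume a full year for everyone.** Section 3.3.1 admits patients up to three months (± 4 weeks) after therapy. Section 3.2.1 ends follow-up about one year after completion of therapy, although section 4.3 counts the year from enrollment. Evaluable status needs only one blood specimen. Suppose, as an assumption, that patients and controls average 0.67 to 0.75 year. Power at 110/330 is then about 90% to 97%, and the IRR detectable with 80% power is about 1.31–1.34 (φ = 1) to 1.62–1.70 (φ = 3). The caution is fair, but the full year is section 6.4's own input and the gap from Table 1 remains. Only if about 45% (50/110) of the planned person-time were realised would the information fall to the 50/150 level.
- **The test behind Table 1 is unknown.** This is true, so exact decimals cannot be confirmed. The two tests differ by at most about 2.4 points at 50/150, far less than the effect of a 2.2-fold larger sample.
- **The rate sentence adds little.** The reference to the entire ALL cohort concerns the rate of 1.88, not the sample size. This is accepted; the finding does not depend on it.

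**Conclusion.** The concern holds. Section 6.4 plans Aim 1 for 110 and 330 and then reports power for 50 and 150 without a reason. This is an inconsistency of inputs, not a miscalculation: Table 1 is sound for the size it uses. For the planned size, the stated powers of 80.0% to 81.2% are too low (about 97% to 99%), and the stated detectable IRRs of 1.45 to 1.90 are too large (about 1.26 to 1.53).

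These figures are approximate. They rest on a full year of follow-up, variance = φ × mean, the rates in section 6.4, and tests that model neither the matching nor clustering by site. The direction follows from the 2.2-fold sample alone. Aim 1 is not underpowered on these inputs.

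**What to change.** Recompute Table 1 and its paragraph for 110 ALL patients and 330 controls, and restate the range of detectable IRRs with the matching healthy-cohort rates. In the same edit, name the test and define the overdispersion parameter so that the table can be reproduced.

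If a comparison of 50 with 150 is really meant, say which patients it covers and why, and bring sections 3.2.2 and 6.3.2 into line. If 50/150 was kept as a deliberate lower bound, say so and show the 110/330 results beside it.

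The cost is one table and one paragraph. If 110/330 is the intended size, enrollment and data collection do not change.

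### Section 6.4 claims sufficient power for any IRR from 1.45 to 1.90, but Table 1 supports each IRR only at or below its own row's overdispersion; the low end falls short if overdispersion is high.

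*Combined protocol and SAP*

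**What the plan says.** Section 6.4 of the combined protocol and SAP contains the only power statement for the Aim 1 comparison of infection rates between ALL patients and matched controls. The ALL rate is assumed to "mirror the currently estimated rate of 1.88 events per person-year", a figure the section describes as "Based on preliminary data collected on this study's cohort of ALL patients". The other inputs are to "assume a two-sided type I error of 0.05, and range the values of overdispersion parameter from 1 to 3". The sample size used is "With 50 ALL patients and 150 matched healthy participants (1:3 match) and one year of follow up on each participant".

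Table 1 has five rows. Each gives a control rate, an IRR, one overdispersion value and a power close to 80%. The text explains the two ends. With no overdispersion, "we will have 80.1% power to detect an IRR of 1.45, i.e., incidence rate of 1.88 for cancer cohort vs. 1.30 for healthy cohort". The other end is introduced by "Under the conservative assumption of a larger overdispersion parameter of 3, we will have 80% power to detect an" IRR of 1.90, against a control rate of 0.99.

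The section then says that the control rate is not accurately known, and that an IRR between 1.45 and 1.90 is "a clinically meaningful effect size for which we will have sufficient power to detect". That sentence does not mention overdispersion.

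The same section plans 110 ALL patients and 330 controls but gives no power at that size.

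**The concern.** Overdispersion is one unknown property of the infection counts, and each row of Table 1 assumes a different value for it. The rows are therefore alternative scenarios: each shows the smallest IRR detectable if that row's overdispersion is the true one. The closing sentence gathers the IRRs from all the scenarios into one range and calls the whole range adequately powered. That holds at the bottom of the range only if overdispersion is near 1, which is the most favourable value considered.

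The plan calls the whole range clinically meaningful and admits that it lacks a good control rate, so a true IRR near 1.45 cannot be set aside. A reader who takes the sentence at face value would credit the study with more power at that end than its own calculation gives.

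**Working it through.** **Inputs (section 6.4).** ALL rate 1.88 per person-year; control rates r0 from Table 1 (1.30, 1.19, 1.11, 1.04, 0.99); one year per person; two-sided alpha 0.05; overdispersion φ from 1 to 3; n1/n0 = 50/150 as in the power paragraph, or 110/330 as planned.

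**Formula.** The plan names no test for this comparison, so I assume a Wald test on the log rate ratio with Poisson variance scaled by φ:

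power = Φ( ln(1.88/r0) / √[φ(1/(1.88·n1) + 1/(r0·n0))] − 1.96 )

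**Step 1: reproduce Table 1 (50/150).**

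| IRR | φ | Stated | Wald | Simulation |
|---|---|---|---|---|
| 1.45 | 1 | 80.1% | 83.6% | 81.8% |
| 1.58 | 1.5 | 81.0% | 83.4% | 82.0% |
| 1.69 | 2 | 80.1% | 82.3% | 81.0% |
| 1.81 | 2.5 | 81.2% | 81.8% | 80.6% |
| 1.90 | 3 | 80.0% | 80.2% | 79.1% |

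The simulation used 40,000 runs, with Poisson counts at φ = 1 and negative binomial counts with variance φ × mean otherwise, and a log rate ratio with robust variance. It agrees with every row to within 2 points. The Wald formula runs up to 3.5 points high, most of all on the 1.45 row, so Wald figures for that IRR are slightly generous.

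**Step 2: IRR 1.45 at φ = 3 (50/150).** ln(1.88/1.30) = 0.3689. The standard error is √[3(1/94 + 1/195)] = 0.2175. The ratio is 1.696, and Φ(1.696 − 1.96) = 39.6%.

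Scaling the plan's own figure avoids my formula. A power of 80.1% corresponds to 0.845 + 1.960 = 2.805 standard errors. Dividing by √3 gives 1.620, and Φ(1.620 − 1.96) = 36.7%. A score test on the rate difference gives 40.8% and the simulation 40.2%. The range is 37 to 41%.

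**Step 3: the grid at 50/150 (Wald, %).**

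| IRR | φ=1 | 1.5 | 2 | 2.5 | 3 |
|---|---|---|---|---|---|
| 1.45 | 83.6 | 67.0 | 54.7 | 45.9 | 39.6 |
| 1.58 | 94.8 | 83.4 | 71.8 | 62.2 | 54.5 |
| 1.69 | 98.3 | 91.5 | 82.3 | 73.3 | 65.5 |
| 1.81 | 99.5 | 95.9 | 89.4 | 81.8 | 74.5 |
| 1.90 | 99.8 | 97.8 | 93.1 | 86.8 | 80.2 |

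Table 1 is the diagonal. Cells to its left exceed 80% and cells to its right do not. At φ = 3 only IRR 1.90 reaches 80%.

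**Step 4: the planned size, 110/330 (Wald, %).** Both arms grow by 110/50 = 2.2.

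| IRR | φ=1 | 1.5 | 2 | 2.5 | 3 |
|---|---|---|---|---|---|
| 1.45 | 99.2 | 94.5 | 86.9 | 78.7 | 71.1 |
| 1.58 | 100.0 | 99.1 | 96.4 | 92.0 | 86.7 |
| 1.69 | 100.0 | 99.9 | 99.0 | 96.9 | 93.8 |
| 1.81 | 100.0 | 100.0 | 99.7 | 98.9 | 97.3 |
| 1.90 | 100.0 | 100.0 | 99.9 | 99.5 | 98.6 |

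For IRR 1.45 at φ = 3, scaling the stated 80.1% gives 2.805 × √(2.2/3) = 2.402, hence 67.1%. The simulation gives 69.7% and the score form 69.9%. Wald gives 71.1% with the rounded control rate, or about 72% with the IRR taken as exactly 1.45. The range is 67 to 72%.

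IRR 1.45 keeps 80% up to φ of about 2.2 (scaled from the plan's figure: 80.1% is almost exactly 80% at φ = 1, and 1 × 2.2 = 2.2) or about 2.45 (Wald, exact IRR). The smallest IRR with 80% power at φ = 3 is about 1.51 (Wald).

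**The case against.** The best defence is that the condition is stated a few lines earlier. The text ties 1.45 to no overdispersion and 1.90 to a value of 3, and Table 1 prints the overdispersion beside each IRR. On that reading the sentence loosely summarises the span of detectable effects across scenarios. This stands as a defence of the table and against any suggestion of concealment. It does not rescue the sentence, which is unconditional and is the one likely to be quoted.

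A second defence is that 110 and 330 will be analysed. This carries real weight: at that size the claim is true over most of the range, though not at the low end under high overdispersion.

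A reader might also infer four stronger things, none of which the documents support:

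- **That each IRR has 80% power at its own row's overdispersion alone.** Power rises as overdispersion falls, so IRR 1.90 has about 80% or more across the whole range of 1 to 3.
- **That the study as planned has less than an even chance of detecting IRR 1.45.** That is so only at 50/150, with overdispersion of about 2.5 or more (Wald). At 110/330 power stays at about 67% or higher. The mismatch between the two sample sizes is a separate issue.
- **That a null result will be taken as evidence against an excess.** No section says so. Section 6.3.2 reports rates with 95% confidence intervals.
- **That the preliminary counts would settle the overdispersion.** Section 6.4 gives only a rate from them, without patient numbers or person-time. Control data are collected only after ALL follow-up ends (section 6.3.2), so dispersion among controls is unknown.

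**Conclusion.** The point holds as a misstatement of what Table 1 shows. The table's figures can be reproduced and are not in error. The fault lies in turning five conditional results into one unconditional claim.

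On the 50/150 basis that section 6.4 uses, the shortfall is large: roughly half the claimed power for IRR 1.45 at the value the plan itself calls conservative. At the planned 110/330 it is modest and confined to the low end of the range under high overdispersion.

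These sizes assume an ALL rate of 1.88, the same overdispersion in both arms, a full year on everyone, and no allowance for matching or loss to follow-up. Section 6.4 states no such allowance either. The choice of test moves the figures by a few points and does not change the conclusion.

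**What to change.** Replace the closing claim in section 6.4 with a conditional one: the smallest IRR detectable with 80% power depends on overdispersion and, for 50 ALL patients and 150 controls, is about 1.45 at overdispersion 1, rising to 1.90 at 3.

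Add the full power grid, IRR 1.45 to 1.90 by overdispersion 1 to 3, at the sample size that will be analysed, and name the test behind it.

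Report the dispersion seen in the preliminary ALL counts, with the number of patients and person-time behind it, as a guide for the ALL arm. Keep the 1 to 3 range, because control dispersion will not be known until those data are drawn.

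The cost is a few lines, one small table and one estimate from data already held. No extra patients are needed. The price is a less favourable stated power at the low end of the range.

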**Study Measures:**

Aim 1 will capture any infection documented at any inpatient or outpatient encounter documented by the managing medical team in the first year after completing ALL chemotherapy. An incident infection rate will be calculated for the cohort and compared with that of age- and sex-matched healthy controls during the same time period. The secondary aim will assess the seroprevalence for pneumococcus, varicella and measles among study subjects at approximately 3, 6, and 12 months after completion of therapy. This aim will also describe B and T lymphocyte subset recovery at these same timepoints. The outcomes for Aim 1 and Aim 2 will be described by certain demographic characteristics and underlying diagnoses, as well as ALL treatment protocol. Additionally, laboratory reports will be prospectively collected. These data will serve to define the infection rate in the first year after completing ALL chemotherapy and inform immune recovery overall and to specific vaccine preventable illnesses (i.e. varicella, measles, and pneumococcus).

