## 1 BACKGROUND INFORMATION AND RATIONALE

### 1.1 Introduction

The treatment modalities of childhood cancer often have a significant impact on the immune system on survivors of childhood cancer. Although there is a robust body of literature that describes immunological outcomes, testing recommendations, and revaccination guidelines after allogeneic hematopoietic cell transplantation (HCT), immunological assessments are not routinely included in surveillance guidelines for survivors of childhood cancer that have not received HCT. As a result, survivorship care providers might not fully consider the impaired recovery of a child's immune system after cancer treatment if the child has not undergone HCT. Currently, survivors of childhood cancer who received standard therapy and missed scheduled vaccinations during their cancer therapy restart their vaccination schedule anywhere between 6 to 12 months after completion of treatment. For patients that completed a vaccine series, the Children's Oncology Group (COG) Hematopoietic Cell Transplant/ Immune/Dermatology Late Effects Taskforce recommends that providers and survivors consider either the use of boosters for previously administered vaccines, or the measurement of titers on which to base the administration of boosters. Despite these recommendations there are limited data on timing of immune reconstitution after ALL chemotherapy and effectiveness of the response to vaccines if administered. It is also acknowledged that there is a paucity of data on the frequency and outcome of infections among survivors in the first year after completion of therapy. Determining the frequency of infection in the first year post chemotherapy and documenting the recovery of immune function overall and to specific vaccine preventable pathogens will provide foundational data to guide current clinical decision-making and inform future clinical trials.

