The proposed multicenter study will serve to define infection rates in the post-ALL therapy period in children, adolescents, and young adults and define the seroprevalence for vaccine specific antigens as well as presence of lymphocyte subsets at discrete time-points after therapy completion. These data will be immediately informative to clinicians aiming to manage expectations of parents for infection risk in their child post ALL therapy. Additionally, this prospective cohort represents an ideal opportunity to compare management decisions for children regarding timing of vaccination following completion of ALL therapy. Currently, The National Comprehensive Cancer Network (NCCN) recommend that survivors of childhood cancer who received standard (non- HCT) therapy and missed scheduled vaccinations during their cancer therapy should be given all vaccinations that were missed, beginning at 6 to 12 months after completion of treatment. Based upon lower-level evidence, the NCCN recommends that survivors of childhood cancer who were fully vaccinated before diagnosis, and who were treated with chemotherapy or radiotherapy (non- HCT), or both, engage with their provider in a shared decision making to determine approaches to revaccination that might be considered for the individual survivor.

One such approach might be to administer booster doses for all routine vaccinations without checking pre-vaccination titers. A different approach would be to measure antibody titers to determine levels of seroprotection first and then recommending booster doses if inadequate levels of seroprotection are found. Finally, in the absence of data for necessity to administer booster dosing, some centers may elect not to measure antibody titers or provider booster dosing. Not surprisingly, these options have led to variability in practice, even when centers have developed institution-specific guidelines. A survey of Canadian pediatric oncology centers found wide variation in the performance of post-treatment titers and reimmunization practices for survivors of ALL who have not had HCT. Data from this descriptive study will serve to inform future comparative trials designed to optimize vaccination protocols in the period after completion of ALL therapy.

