### **4.2 Visit schedule**

#### **4.2.1 Visit**

Once enrolled, subjects will have a baseline visit, followed by in-person visits at approximately 3, 6, and 12 months. Prior to or at the time of the baseline visit, vaccination records will be obtained. At the baseline and follow-up visits an interim infectious history will be obtained. Patients will have blood drawn for research assays as detailed below at 3-, 6-, and 12-month visits.

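### Seroprevalence at 12 months, and possibly at 6 months, can include response to post-therapy vaccine doses, so it cannot by itself show protection retained from vaccination before diagnosis

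*Combined protocol and SAP*

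**What the plan says.** **Interpretation.** Section 6.4 states: "The point estimates for seroprevalence will inform if children retain protection against specific pathogens from vaccination administered prior to their diagnosis". It then says the immune-function data will inform whether revaccination is needed.

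**Endpoint.** Section 6.1 defines the Aim 2a endpoint as the proportion with antibody to each pathogen at each timepoint. It sets no condition on later vaccination.

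**Splits.** Section 6.3.3 names demographics, primary series completed or not before chemotherapy, and blinatumomab. The abstract adds: "The outcomes for Aim 1 and Aim 2 will be described by certain demographic characteristics and underlying diagnoses, as well as ALL treatment protocol". Section 6.4 leaves the list open: "by subsets of patient characteristics (e.g., chemotherapy inclusive of blinatumomab". The primary-series split is the only one that concerns vaccines.

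**Post-therapy vaccination.** Section 1.1 says survivors who "missed scheduled vaccinations during their cancer therapy restart their vaccination schedule anywhere between 6 to 12 months after completion of treatment". Section 1.2 reports the guideline position that such survivors "should be given all vaccinations that were missed, beginning at 6 to 12 months after completion of treatment". For fully vaccinated survivors, section 1.2 lists boosting everyone, boosting neither with nor after titers, or an approach to "measure antibody titers to determine levels of seroprotection first and then recommending booster doses if inadequate levels of seroprotection are found". It gives no timing for these and says practice varies.

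**Vaccination data.** Section 4.2.1 says: "Prior to or at the time of the baseline visit, vaccination records will be obtained". The follow-up update named there is infectious history. Section 5.1.1 lists vaccination records among the abstracted variables, and section 4.3 has chart abstraction running through the observational period.

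**The concern.** A positive antibody result at 12 months can arise in two ways. The child may have kept or regained antibody from pre-diagnosis vaccination, or may have responded to a dose given after therapy. Section 6.4 attributes the result to the first source, but the planned analysis does not distinguish the two.

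This bears on the main question of Aim 2a. Section 1.2 faults earlier studies for not allowing for better immune recovery further from therapy, so a rise from 3 to 12 months is the signal sought. New doses can produce the same rise. If they are counted as retention, children look better protected without revaccination than they are, and revaccination looks less necessary. Section 1.2 also says "this prospective cohort represents an ideal opportunity to compare management decisions for children regarding timing of vaccination following completion of ALL therapy", yet section 6 contains no analysis that uses vaccination timing.

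**Working it through.** There is no plan figure to reproduce. Section 6.4 gives power for Aim 1 only and treats Aim 2 as descriptive.

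**Step 1: set the draws against the restart window.** The window is 6 to 12 months after therapy (1.1, 1.2).

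| Draw | Counted from end of therapy | Counted from enrollment |
|---|---|---|
| 3 months | before the window | 0 to 6 months after therapy |
| 6 months | at its opening | 3 to 9 months |
| 12 months | at its close | 9 to 15 months |

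The last column adds the draw time to an enrollment date from 3 months before to 3 months after end of therapy (3.3.1). It ignores the 4-week tolerance, which widens each range by about a month at either end. On the first reading, the 12-month draw is exposed, the 6-month draw possibly, and the 3-month draw hardly at all.

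**Step 2: does any named split isolate new doses?** The primary-series split classifies patients by doses before chemotherapy. It does not identify who was dosed afterwards. Patients with an incomplete series are plausible candidates for catch-up, so that comparison could itself be affected.

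**Step 3: illustrate the size when dosing is unrelated to serostatus.** All rates are assumptions, because the documents give none. Let s be the true retained proportion (0.3, 0.5, 0.7), f the share dosed before the draw, and q the share of dosed seronegatives who respond (0.6, 0.8, 0.9). Serostatus is otherwise taken as stable.

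- Pooled proportion: p = s + (1 − s)fq, so the overstatement is (1 − s)fq.
- 95% interval: p ± 1.96 × √(p(1 − p)/n).
- Example: f = 0.25, s = 0.3, q = 0.9 gives 0.7 × 0.25 × 0.9 = 0.158. The half-width at n = 110 is 0.093.

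| Share dosed | Overstatement (points) | Interval excludes s, n = 110 | Same, n = 66 |
|---|---|---|---|
| 5% | 1 to 3 | 0 of 9 | 0 of 9 |
| 10% | 2 to 6 | 0 of 9 | 0 of 9 |
| 25% | 5 to 16 | 5 of 9 | 2 of 9 |
| 50% | 9 to 32 | 9 of 9 | 8 of 9 |

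The n = 66 column is an assumed completed-series stratum, 60% of 110.

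**Step 4: would dropping dosed patients solve it?** Not if boosting follows titers. This is an extreme case, and it needs clinical titers, because study results are not available to clinicians in real time (5.1.2.1). Take s = 0.6, q = 0.8, and a share g of seronegatives dosed.

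- Pooled, s + (1 − s)gq: 0.76 at g = 0.5; 0.84 at g = 0.75.
- Undosed only, s/(s + (1 − s)(1 − g)): 0.6/0.8 = 0.75; 0.6/0.7 = 0.86.
- Last pre-dose result for dosed patients, combined with never-dosed patients: 0.60 in both, if every dosed patient has a pre-dose sample.
- If half of the dosed patients have none, s/(1 − 0.5(1 − s)g): 0.6/0.9 = 0.67; 0.6/0.85 = 0.71.

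Pre-dose results are therefore the better basis, and the number of patients without one has to be reported.

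**The case against.** The strongest reply is that Aim 2 is secondary and descriptive, and that a proportion at each visit is a legitimate description. That stands for the proportion. It does not cover the retention sentence in 6.4, which attributes the antibody to a source.

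Three stronger readings are tempting, and the documents do not support them.

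- **Post-therapy doses will go unrecorded.** Section 4.2.1 alone might suggest this. But 3.2.1 has the chart examined for vaccination history, 4.3 has abstraction during follow-up, 5.1.1 lists vaccination records, and 6.3.4 collects vaccination histories to monitor balance with controls. Capture during follow-up is likely. What is missing is a stated update, with dates, through each draw. Nor is a dose split ruled out, since the list in 6.4 is open; it is simply not named.
- **All three draws are compromised.** The abstract, Figure 1, 2.2 and 5.1.2.1.3 count the draws from end of therapy, and 3.2.1 ends follow-up about a year after therapy. On that clock the 3-month sample precedes the restart window. Even counted from enrollment it falls at about 0 to 6 months. The timing of boosters for fully vaccinated survivors is not given, so a few early doses cannot be excluded.
- **The bias is known to be large.** No retention, uptake or response rate is given. Nothing places dosing at 25% or 50% rather than 10%, and no boosting at all is one of the options in 1.2.

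It is also fair to say that a pre-dose figure has its own errors, because samples come at different times since therapy. In the step 4 setting, if 10% to 20% of seronegatives later recover unaided, it is low by (1 − s)g times that share, or 2 to 6 points. If 10% to 20% of seropositives later wane and 25% to 50% are dosed regardless of serostatus, it is high by s × share dosed × share waning, or 1.5 to 6 points.

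**Conclusion.** The point holds for the retention reading of the 12-month proportion, and possibly the 6-month one. The direction is known: response to new doses can only raise the proportion. The size is not. Under dosing unrelated to serostatus, 30% to 70% true retention and 60% to 90% response, the overstatement is negligible against sampling error at 10% dosing or less. It becomes material somewhere around 25%, and exceeds the half-width of the n = 110 interval in every case examined at 50%. The plan should be changed, because its stated inference does not follow from its stated analysis. A reader should not infer that the seroprevalence endpoint is invalid.

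**What to change.** 1. **Section 4.2.1:** clarify that the vaccination-record abstraction already listed in 5.1.1 runs through each blood draw, with dose dates.
2. **Section 6.3.3:** keep the all-patient proportion as serostatus under current practice. For each pathogen at 6 and 12 months, add a split by whether a post-therapy dose of that vaccine preceded the draw.
3. **Section 6.4:** base the retention statement on samples drawn before any post-therapy dose, among patients vaccinated against that pathogen before diagnosis. That means the 3-month sample, and later samples only while the patient is undosed, with the last pre-dose result used for patients dosed later. Report time since end of therapy and the number of dosed patients with no pre-dose sample. No baseline blood is planned (4.2.1) and one specimen makes a patient evaluable (3.2.2), so some may have none. Note that later undosed-only figures can overstate retention if boosting was titer-guided.
4. **Separately, reconcile the time origin.** The draws count from end of therapy in the abstract, Figure 1, 2.2 and 5.1.2.1.3, but from meeting the inclusion criteria in 5.1.2.1, although that wording may be meant as a condition. Follow-up ends a year after therapy in 3.2.1 and a year after enrollment in 4.3.

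This needs no new visits or samples and leaves vaccination practice untouched. It adds 3 × 2 × 2 = 12 descriptive proportions and one retention figure per pathogen. The price is precision. If 25% of 110 were dosed, the groups would be about 82 and 28. At an assumed proportion of 60%, 1.96 × √(0.6 × 0.4/n) gives half-widths of 10.6 and 18.1 points, against 9.2 for all 110. Pre-dose samples would also come at differing times since therapy.
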